### **12.9.1.3. Sample Size Determination**

The total sample size is estimated to be approximately 80 participants for the Sub-Study A Phase 1b/2.

#### **12.9.1.3.1. Phase 1b Dose Finding**

Approximately 9-18 participants will be enrolled in the Phase 1b part. However, the total number of participants will depend on the number of dose levels needed to determine the MTD/RP2D of each combination and the number of participants evaluable for DLT at each dose level.

Beginning with the first dose level, participants will be enrolled, treated, and monitored in cohorts of 3-6 participants during the 28-day DLT evaluation period (Cycle 1). A minimum of 9 participants and up to approximately 18 participants will be enrolled to evaluate DLTs during the first cycle of treatment.

#### **12.9.1.3.2. Phase 2 Dose Expansion**

Approximately 62 participants will be enrolled in the Phase 2 part of Sub-Study A.

Phase 2 will test the null hypothesis that the durable ORR does not exceed 35% ( $H_0$ : durable ORR  $\leq 35\%$ ). The null hypothesis will be tested against the alternative ( $H_1$ : durable ORR  $> 35\%$ ) at one-sided level of significance  $\alpha = 0.025$  using the binomial distribution.

Sixty-two (62) participants will provide at least 90% power to reject the null hypothesis if the true durable ORR is at least 55% (durable ORR  $\geq 55\%$ ).

At the end of Phase 2:

- If there are  $\leq 29$  objective durable responders of 62 participants in the Phase 2 part, then it will be declared that the null hypothesis cannot be rejected.
- If there are  $\geq 30$  objective durable responders of 62 participants in the Phase 2 part, then the null hypothesis will be rejected.

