#### **12.9.1.5. General Considerations**

##### **12.9.1.5.1. Primary Endpoints**

###### **Phase 1b**

The primary safety endpoint in Phase 1b is DLTs. Refer to [Section 9.4.2](#).

The occurrence of DLTs and AEs constituting DLTs will be summarized for participants in the Phase 1b part as described in [Section 12.3](#).

## Phase 2

The primary efficacy endpoint in the Phase 2 part is Durable OR. Refer to [Section 12.3](#).

Durable ORR will be calculated along with the 2-sided 95% CI for durable ORR using the Clopper-Pearson method. Participants who do not have a post-baseline tumor assessment due to early progression of disease, who receive anti-cancer therapies other than the study treatments prior to reaching a CR or PR for 10 months, or who die, have PD, or stop tumor assessments for any reason prior to reaching a CR or PR for 10 months will be counted as non-responders in the assessment of durable OR.

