### 12.9.1.5.4. Interim Analysis

A futility analysis based on ORR will be performed to allow early termination for futility after 30 participants are treated and followed for 2 on-treatment assessments (~4 months), without holding participant enrollment. If based on the observed ORR the probability of a true ORR  $\geq 48\%$  is  $\leq 0.10$ , then the study will be stopped for futility. For example, the study will be stopped for futility if  $\leq 10$  confirmed ORs are observed in the first 30 participants treated.

The probability of stopping the sub-study (if  $\leq 10$  confirmed ORs are observed in the first 30 participants treated) under the alternative hypothesis is 0.014.

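### Sub-Study A Phase 2: the exact binomial test with 30 of 62 has 88.0% power at a durable ORR of 55%, not the stated minimum of 90%

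*Protocol*

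**What the plan says.** Section 12.9.1.3.2 (Phase 2 Dose Expansion) gives the whole design.

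- Null hypothesis: "Phase 2 will test the null hypothesis that the durable ORR does not exceed 35" percent.
- Test: "one-sided level of significance $\alpha = 0.025$ using the binomial distribution".
- Sample size and power: "Sixty-two (62) participants will provide at least 90% power to reject the null hypothesis if the true durable ORR is at least 55" percent.
- Decision rule: with 30 or more "objective durable responders of 62 participants in the Phase 2 part, then the null hypothesis will be rejected". With 29 or fewer, the null is not rejected.

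Section 12.9.1.5.1 analyses the endpoint with a Clopper-Pearson interval. Participants who "stop tumor assessments for any reason prior to reaching a CR or PR for 10 months will be counted as non-responders", so the denominator is everyone treated.

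Section 12.9.1.5.4 adds a futility look, run "without holding participant enrollment". The sub-study stops if 10 or fewer "confirmed ORs are observed in the first 30 participants treated". The stated probability of this under the alternative is 0.014.

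**The concern.** The null rate, alpha, test, sample size and cut-off are all fixed, so power at 55% is a single number that can be computed. The protocol presents 90% as a floor over all true rates of 55% or more. Power rises with the true rate, so the floor has to hold at exactly 55%, and there the exact binomial tail falls below 90%.

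This is the only formal efficacy test with a stated power in the protocol; Phase 2 of Sub-Study B is sized on the precision of an ORR estimate (Section 13.9.1.3.2). The power statement is also the only justification given for 62 participants. If it is wrong, the risk of missing a treatment that reaches the target rate is understated.

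**Working it through.** **Inputs, all from Section 12.9.1.3.2:** n = 62, p0 = 0.35, p1 = 0.55, one-sided alpha = 0.025, reject if X ≥ 30.

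**1. Where the 90% comes from.** The normal approximation without continuity correction is

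power = Φ{ [ (p1 − p0)√n − z(0.975)·√(p0(1 − p0)) ] / √(p1(1 − p1)) }

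- (p1 − p0)√n = 0.20 × 7.874 = 1.5748
- z(0.975)·√(0.35 × 0.65) = 1.960 × 0.4770 = 0.9348
- √(0.55 × 0.45) = 0.4975
- (1.5748 − 0.9348) / 0.4975 = 1.286, and Φ(1.286) = 0.9008

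Solving the same formula for 90% power gives n = 61.8, which rounds up to 62. Both the stated n and the stated power therefore come out of this approximation. With a continuity correction it gives 0.8767.

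**2. The test the protocol specifies.** With X ~ Binomial(62, p), the tail is P(X ≥ r) = Σ over k = r to 62 of C(62, k)·p^k·(1 − p)^(62 − k).

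| Cut-off r | P(X ≥ r) at 0.35 (alpha) | P(X ≥ r) at 0.55 (power) |
|---|---|---|
| 29 | 0.0370 | 0.9232 |
| **30** | **0.0205** | **0.8797** |
| 31 | 0.0107 | 0.8211 |

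Thirty is the lowest cut-off with alpha at or below 0.025. The Clopper-Pearson interval agrees: its lower 95% limit is 0.3550 for 30/62 and 0.3398 for 29/62, so the interval first excludes 35% at 30. Power at 55% is 88.0%, and the type II error is 1 − 0.8797 = 12.0%.

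**3. Rate at which the stated rule has 90% power.** Solving P(X ≥ 30 | 62, p) = 0.90 gives p = 0.557.

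**4. Nearby sample sizes,** each with the lowest cut-off that keeps exact alpha at or below 0.025:

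| n | Cut-off | Alpha | Power at 55% |
|---|---|---|---|
| 60 | 29 | 0.0228 | 87.8% |
| 61 | 30 | 0.0158 | 85.1% |
| 62 | 30 | 0.0205 | 88.0% |
| 63 | 31 | 0.0141 | 85.3% |
| 64 | 31 | 0.0184 | 88.1% |
| 65 | 31 | 0.0236 | 90.4% |
| 66 | 32 | 0.0165 | 88.2% |
| 67 | 32 | 0.0212 | 90.5% |
| 68 | 33 | 0.0148 | 88.4% |
| 69 | 33 | 0.0190 | 90.6% |

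No n from 55 to 64 reaches 90%. From 69 to 79, the largest size checked, power stays above 90%.

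**5. Futility look.** P(X ≤ 10 | 30, 0.55) = 0.0138, which reproduces the protocol's 0.014. That figure is therefore an exact binomial probability with the ORR set at 55%. If ORR and durable ORR were the same endpoint at 55%, and the stop were binding, power would be

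Σ over x = 11 to 30 of P(X1 = x | 30, 0.55)·P(X2 ≥ 30 − x | 32, 0.55) = 0.8768.

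This is a worst case, because ORR cannot be below durable ORR. At an ORR of 64%, the stopping probability is 0.0006, so the loss is at most 0.06 points.

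**The case against.** The strongest objection concerns importance. The gap is 2 points in a planning statement. Type I error is controlled, 30 is the correct cut-off for 62, and the decision rule is unambiguous. Section 2 describes the study as primarily exploratory, and this is a single-arm, open-label Phase 2 part, where a type II error of 12% instead of 10% is tolerable. All of this stands: correcting the figure changes no participant's treatment and no analysis.

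It does not rescue the statement. The protocol gives at least 90% as a guarantee, and the test it names does not meet it.

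Two other defences fail:

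- **Enrolment is only approximately 62.** The cut-off is defined for exactly 62, and no size from 55 to 64 reaches 90%.
- **Dropout.** Those who stop assessments early count as non-responders, so the denominator does not shrink.

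One caution is fair. The futility look uses confirmed ORR, not durable ORR. Its extra cost in power depends on how far ORR exceeds durable ORR and may be practically nil, so it should not be described as a fixed further loss.

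**Conclusion.** The power statement is wrong as written. The stated rule has 88.0% power at a durable ORR of 55%, so the type II error is 12.0%, about one-fifth above the 10% maximum implied. The rule reaches 90% power only at a true rate of about 55.7%. No cut-off at 62 gives both alpha at or below 0.025 and 90% power at 55%.

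This result needs only the inputs in Section 12.9.1.3.2 and the binomial distribution named there. The 87.7% with futility stopping additionally assumes that ORR equals durable ORR at 55% and that the stop is binding. The consequence is small: the decision rule and type I error control are sound, and only the stated power, and with it the justification for 62, needs correcting.

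**What to change.** Keep 62 participants and the cut-off of 30. In Section 12.9.1.3.2, replace the power claim with: approximately 88% power (exact binomial) at a true durable ORR of 55%, and 90% power at about 55.7%. If the futility look is mentioned, say that it lowers power to no less than 87.7% at 55%, and by a negligible amount if the ORR is near 64%. The cost is one sentence, repeated in the SAP if the figure also appears there, and a slightly less favourable number.

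If 90% at 55% has to stand, the smallest exact design is 65 participants with a cut-off of 31 (alpha 0.0236, power 90.4%). That adds three participants and changes the counts in Sections 12.4, 12.4.2 and 12.9.1.3. It is sensitive to the final number treated: power falls back to 88.2% at 66 and 88.4% at 68. With approximate enrolment, either fix the analysed number at 65 or plan for at least 69, and state the cut-off for each possible final size.

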#### **12.9.1.4. Analysis Set**

Refer to [Section 9.3](#) for analysis sets.

#### **12.9.1.5. General Considerations**

##### **12.9.1.5.1. Primary Endpoints**

###### **Phase 1b**

The primary safety endpoint in Phase 1b is DLTs. Refer to [Section 9.4.2](#).

The occurrence of DLTs and AEs constituting DLTs will be summarized for participants in the Phase 1b part as described in [Section 12.3](#).

## Phase 2

The primary efficacy endpoint in the Phase 2 part is Durable OR. Refer to [Section 12.3](#).

Durable ORR will be calculated along with the 2-sided 95% CI for durable ORR using the Clopper-Pearson method. Participants who do not have a post-baseline tumor assessment due to early progression of disease, who receive anti-cancer therapies other than the study treatments prior to reaching a CR or PR for 10 months, or who die, have PD, or stop tumor assessments for any reason prior to reaching a CR or PR for 10 months will be counted as non-responders in the assessment of durable OR.

### 12.9.1.5.2. Secondary Endpoints

#### 12.9.1.5.2.1. Efficacy Analyses

Additional efficacy endpoints, durable OR (Phase 1b; refer to [Section 12.9.1.5.1](#)), OR (Phase 1b and Phase 2), TTR (Phase 2), DR (Phase 2), and PFS (Phase 2) will be summarized based on investigator assessment using RECIST v1.1. OS will be summarized for Phase 2.

- OR is defined as a CR or PR according to RECIST v1.1 based on investigator assessment. Both CR and PR must be confirmed by repeat assessments performed no less than 4 weeks after the criteria for response are first met. Only tumor assessments performed on or before the start date of any further anti-cancer therapies will be considered in the assessment.
- TTR is defined for participants with confirmed objective response (CR or PR) as the time from the date of first dose to the date of first documentation of objective tumor response which is subsequently confirmed.
- DR is defined for participants with confirmed objective response (CR or PR) as the time from the first documentation of OR to the first documentation of objective tumor progression or to death due to any cause, whichever occurs first. The censoring rules for DR are as described below for PFS but participants will not be censored in the analysis of DR due to no adequate baseline assessment as only participants with OR are included in the analysis of DR.
- PFS is defined as the time from the date of first dose of study treatment to the date of first documentation of PD or death due to any cause, whichever occurs first. PFS data will be censored on the date of the last adequate tumor assessment for participants who do not have an event (PD or death), for participants who start new anti-cancer treatment prior to an event, or for participants with an event after 2 or more missing tumor assessments. Participants who do not have an adequate baseline tumor assessment or who do not have any adequate post-baseline tumor assessments per RECIST v1.1 will be censored on the date of first dose unless death occurred on or before the time of the second planned tumor assessment in which case the death will be considered an event.

- OS is defined as the time from the date of first dose of study treatment to the date of death due to any cause. Participants last known to be alive will be censored at the date of last contact.

TTR will be summarized using simple descriptive statistics (eg, median and range). OR will be summarized as the proportion of participants in the analysis population with OR and corresponding 2-sided 95% CI using the Clopper-Pearson method. DR, PFS, and OS will be analyzed using Kaplan-Meier methods. Point estimates will be presented with 95% CIs.

#### **12.9.1.5.2.2. Safety Analyses**

For Phase 1b primary safety analysis, refer to [Section 12.3](#) for DLT.

For Phase 1b and Phase 2 secondary safety analyses, refer to [Sections 9.4.3.2](#) and [9.4.5](#).

#### **12.9.1.5.2.3. PK Analyses**

Refer to master protocol [Section 9.4.3.3](#) for the analysis of PK endpoints for sasanlimab.

Trough concentrations for encorafenib, binimetinib and any analyzed metabolites will be summarized descriptively (n, mean, SD, coefficient of variation [CV], median, minimum, maximum, geometric mean, its associated CV, and 95% confidence interval) by cohort/dose and cycle/ day. Exclusions or separate summaries for dose modifications and concomitant medications may be considered in data summaries.

Dose-normalized PK parameters ( $C_{\text{trough-DN}}$ ) may be reported as appropriate.

#### **12.9.1.5.2.4. Immunogenicity Analyses**

Refer to master protocol [Section 9.4.3.4](#) for the analysis of immunogenicity endpoint.

#### **12.9.1.5.2.5. Biomarker Analyses**

Refer to master protocol [Section 9.4.4.1](#) for the analysis of biomarker endpoints.

#### **12.9.1.5.2.6. Patient Reported Outcomes Analyses**

The EORTC QLQ-C30 and EORTC QLQ LC13 will be scored according to its user guide/scoring manual.

At each time point, the number and percentage of participants who complete the EORTC QLQ-C30 and EORTC QLQ-LC13 will be summarized, as will the reasons for non-completion of these measures. An instrument is considered complete if at least one item was answered by the participant.

Summary statistics (mean and standard deviation [SD], median, range, and 95% CI) of absolute scores will be reported for each of the total and subscales of the EORTC QLQ-C30 and the EORTC QLQ-LC13. The mean change from baseline with 95% CI will also be reported by time point.

### 12.9.1.5.3. Exploratory Endpoints

Refer to [Section 9.4.4](#) for biomarker exploratory endpoints.

Depth of response is defined as a reduction in tumor burden in target lesions. Summary statistics for depth of response (n, %) will be determined and further described in the SAP.

### 12.9.1.5.4. Interim Analysis

A futility analysis based on ORR will be performed to allow early termination for futility after 30 participants are treated and followed for 2 on-treatment assessments (~4 months), without holding participant enrollment. If based on the observed ORR the probability of a true ORR  $\geq 48\%$  is  $\leq 0.10$ , then the study will be stopped for futility. For example, the study will be stopped for futility if  $\leq 10$  confirmed ORs are observed in the first 30 participants treated.

The probability of stopping the sub-study (if  $\leq 10$  confirmed ORs are observed in the first 30 participants treated) under the alternative hypothesis is 0.014.

## 12.10. Supporting Documentation and Operational Considerations for Sub-Study A

### 12.10.1. Clinical Laboratory Tests for Sub-Study A

In addition to the clinical laboratory tests required in Master Protocol [Section 10.2](#), the tests in Table 11 will be required for participants in Sub-Study A:

**Table 11. Clinical Laboratory Tests Added for Sub-Study A**

Hematology	Chemistry	Urinalysis

 
• Hematocrit
 
• RBC
 
	
 
• CK (If total CK <math>\geq 3 \times</math> ULN, then measure isoenzymes, serum creatinine and myoglobin in blood weekly)
 
• Direct bilirubin if total bilirubin values are above ULN
 
	
 
• Appearance
 
• Color
 
• Specific gravity
 
• pH
 
• Glucose
 
• Ketones
 
• Nitrite
 
• Leukocytes
 
• Microscopic analysis (Reflex Testing)a
 

a. Only if urine dipstick is positive for nitrites or leukocytes.

### **12.10.2. Contraceptive Guidance for Sub-Study A**

On the basis of the mechanism of action of sasanlimab and data from approved drugs of the same class, sasanlimab may cause a risk for severe manifestations of developmental toxicity in humans; studies to evaluate the development toxicity of sasanlimab have not been conducted. Therefore, the use of a highly effective method of contraception is required

#### **12.10.2.1. Male Participant Reproductive Inclusion Criteria**

Male participants are eligible to participate if they agree to the following requirements during the intervention period and for at least 6 months after the last dose of study intervention, which corresponds to the time needed to eliminate reproductive safety risk of the study intervention(s):

- Refrain from donating sperm.

PLUS either:

- Be abstinent from heterosexual intercourse with a female of childbearing potential as their preferred and usual lifestyle (abstinent on a long-term and persistent basis) and agree to remain abstinent.

OR

- Must agree to use a male condom when engaging in any activity that allows for passage of ejaculate to another person.
- In addition to male condom use, a highly effective method of contraception may be considered in WOCBP partners of male participants (refer to the list of highly effective methods below in [Section 12.10.2.4](#)).

#### **12.10.2.2. Female Participant Reproductive Inclusion Criteria**

A female participant is eligible to participate if she is not pregnant or breastfeeding, and at least 1 of the following conditions applies:

- Is not a WOCBP (see definitions below in [Section 12.10.2.3](#)).

OR

- Is a WOCBP and using a contraceptive method that is highly effective (with a failure rate of <1% per year), preferably with low user dependency, as described below during the intervention period and for at least 6 months after the last dose of study intervention, and agrees not to donate eggs (ova, oocytes) for the purpose of reproduction during this period, which corresponds to the time needed to eliminate any reproductive safety risk of the study intervention(s). If the chosen highly effective method is a hormonal method, then the use of at least 1 form of non-hormonal contraception is required (see [Section 12.10.2.4](#)).

The investigator is responsible for review of medical history, menstrual history, and recent sexual activity to decrease the risk for inclusion of a woman with an early undetected pregnancy.

### **12.10.2.3. Woman of Childbearing Potential (WOCBP)**

A woman is considered fertile following menarche and until becoming postmenopausal unless permanently sterile (see below).

If fertility is unclear (eg, amenorrhea in adolescents or athletes) and a menstrual cycle cannot be confirmed before the first dose of study intervention, additional evaluation should be considered.

Women in the following categories are not considered WOCBP

1. Premenopausal female with 1 of the following:

- Documented hysterectomy;
- Documented bilateral salpingectomy;
- Documented bilateral oophorectomy.

For individuals with permanent infertility due to an alternate medical cause other than the above, (eg, mullerian agenesis, androgen insensitivity), investigator discretion should be applied to determining study entry.

Note: Documentation for any of the above categories can come from the site personnel's review of the participant's medical records, medical examination, or medical history interview. The method of documentation should be recorded in the participant's medical record for the study.

2. Postmenopausal female:

- A postmenopausal state is defined as no menses for 12 months without an alternative medical cause. In addition, a
  - high FSH level in the postmenopausal range must be used to confirm a postmenopausal state in women under 60 years of age and not using hormonal contraception or HRT.
  - Female on HRT and whose menopausal status is in doubt will be required to use one of the non-estrogen hormonal highly effective contraception methods if they wish to continue their HRT during the study. Otherwise, they must discontinue HRT to allow confirmation of postmenopausal status before study enrollment.

#### **12.10.2.4. Contraception Methods**

Contraceptive use by men or women should be consistent with local availability/regulations regarding the use of contraceptive methods for those participating in clinical trials.

##### **Highly Effective Methods That Have Low User Dependency**

1. Implantable progestogen-only hormone contraception associated with inhibition of ovulation\*.
2. Intrauterine device.
3. Intrauterine hormone-releasing system\*.
4. Bilateral tubal occlusion.
5. Vasectomized partner.
  - Vasectomized partner is a highly effective contraceptive method provided that the partner is the sole sexual partner of the WOCBP and the absence of sperm has been confirmed. If not, an additional highly effective method of contraception should be used. The spermatogenesis cycle is approximately 90 days.

##### **Highly Effective Methods That Are User Dependent**

1. Combined (estrogen and progestogen-containing) hormonal contraception associated with inhibition of ovulation\*:
  - Oral;
  - Intravaginal;
  - Transdermal.
2. Progestogen-only hormone contraception associated with inhibition of ovulation\*:
  - Oral;
  - Injectable.
3. Sexual abstinence:
  - Sexual abstinence is considered a highly effective method only if defined as refraining from heterosexual intercourse during the entire period of risk associated with the study intervention. The reliability of sexual abstinence needs to be evaluated in relation to the duration of the study and the preferred and usual lifestyle of the participant.

\*There is a potential for encorafenib to induce CYP3A4, which may reduce the effectiveness of hormonal contraception methods. Therefore, the use of at least 1 form of non-hormonal contraception is required for females of childbearing potential. One of the following acceptable barrier methods must be used in addition to any of the hormonal highly effective methods listed above:

- Male or female condom with or without spermicide;
- Cervical cap, diaphragm, or sponge with spermicide;
- A combination of male condom with either cervical cap, diaphragm, or sponge with spermicide (double-barrier methods).

